12.3 Interim Analysis

No formal interim analysis is planned.

12.4 Determination of Sample Size

Due to exploratory nature of this study, a sample size of 8 subjects per cohort is empirically determined and consistent with typical sample sizes used for similar studies to assess PK and safety data.

13.0 QUALITY CONTROL AND QUALITY ASSURANCE

13.1 Monitoring

The study will be monitored by ProSciento's monitor.

Monitoring visits to the CRU will be made periodically during the study to ensure that all aspects of the protocol and GCP are followed, CRFs are completed correctly, and drug accountability is monitored. The Monitor will visit the CRU at least once before First Subject First Visit (FSFV) (Initiation Visit), at least once during the clinical part of the study, and at least once after Last Subject Last Visit (LSLV). Furthermore, the Monitor must be available for discussions by telephone.

ProSciento may assign additional Clinical Research Associates (CRAs)/Monitors on an ad hoc basis for training purposes and to meet required timelines. In addition, if study timelines are modified for any reason, e.g., delays in recruitment or accelerated enrollment, ProSciento may use additional CRAs at its discretion to ensure study expectations are met.

The Monitor must be given direct access to source documents, such as original documents, data, and records. Direct access includes permission to examine, analyze, verify any record(s) and report(s) that are important to evaluation of the clinical study. The study will be monitored to verify integrity and validity of the data. Monitoring will follow a Monitoring Plan.

Additional QC monitoring of the clinical study for protocol and GCP compliance will be conducted periodically by qualified staff of ProSciento.

13.2 Protocol Deviations

The Investigator should not deviate from the protocol, except where necessary to eliminate an immediate hazard to study subjects. Should other circumstances arise that will require deviation from protocol-specified procedures, unless there is an emergency or immediate need, the Investigator should contact the medical monitor and Sponsor to review and discuss the implications of the deviation and determine the appropriate course of action. Any deviation must be documented, stating the reason and date, the action taken, and the impact for the subject and/or the study. The documentation must be kept in the Investigator's Study File and the Sponsor's Study Master File.

14.0 ETHICAL ASPECTS OF THE STUDY

This study will be conducted in accordance with the Protocol, the International Conference on Harmonization (ICH), Guideline for Good Clinical Practice: Consolidated Guidance (E6) and applicable regulatory requirements including clinical research guidelines established by the Basic Principles defined in the U.S. 21 CFR Parts 50, 56, and 312 and the principles enunciated in the Declaration of Helsinki (revised version Fortaleza 2013). 7.8

14.1 Institutional Review Board and/or Independent Ethics Committee

Prior to commencement of the study, the protocol, any amendments, subject information/informed consent form, any other written information to be provided to the subject, subject recruitment procedures, information about payments and compensation available to subjects if not mentioned in the subject information, the Investigator's current CV and/or other documentation evidencing qualifications, and other documents as required by the local Independent Ethics Committee (IEC)/Institutional Review Board (IRB) should be submitted. The submission letter should clearly identify (by study identification number, including version, title and/or date of the document) which documents have been submitted to the IEC/IRB. Written approval/favorable opinion must be obtained from IEC/IRB prior to commencement of the clinical study start.

During the study, the Investigator must promptly report the following to the IEC/IRB: Updates to IB, unexpected SAEs where a causal relationship cannot be ruled out, substantial amendments to the protocol, non-substantial amendments, deviations to the protocol implemented to eliminate immediate hazards to the subjects, new information that may affect adversely the safety of the subjects or the conduct of the study (including new risk/benefit analysis in case it will have an impact on the planned follow-up of the subjects), annually written summaries of the study status and other documents as required by the local IEC/IRB.

Substantial amendments must not be implemented before approval/favorable opinion, unless necessary to eliminate hazards to the subjects.

The Investigator must maintain an accurate and complete record of all submissions made to the IEC/IRB. The records should be filed in the Investigator's Study File and copies must be provided to the Sponsor.

14.2 Regulatory Authorities

Regulatory Authorities will receive the Clinical Study Application, Protocol, Amendments to the Protocol, reports on SAEs and the Integrated Clinical Study Report according to national regulations.

14.3 Responsibilities of the Investigator

The Investigator will conduct this clinical study in compliance with all applicable national, state, local or regional laws and regulatory requirements of the countries in Version 4.0_06Apr2018

which the clinical study is performed. The Investigator will align his or her conduct in accordance with the "Responsibilities of the Investigator".

Clinical research studies sponsored by the Sponsor are subject to ICH GCP and all the applicable local laws and regulations. The responsibilities imposed on Investigators by the FDA are summarized in the "Statement of Investigators" (Form FDA 1572), which must be completed and signed before the Investigator may participate in this study.

14.4 Informed Consent

Once signed, the original informed consent form, subject authorization form (if applicable), and subject information sheet (if applicable) will be stored in the Investigator's site file. The Investigator must document the date the subject signs the informed consent in the subject's medical record. Copies of the signed informed consent form, the signed subject authorization form (if applicable), and subject information sheet (if applicable) shall be given to the subject.

All revised informed consent forms must be reviewed and signed by relevant subjects or the relevant subject's legally acceptable representative in the same manner as the original informed consent. The date the revised consent was obtained should be recorded in the subject's medical record, and the subject should receive a copy of the revised informed consent form.

14.5 Subject Confidentiality

The Sponsor and designees affirm and uphold the principle of the subject's right to protection against invasion of privacy. Subject records will be kept private except when ordered by law. The following individuals will have access to study subject records: Principal Investigator and designees, study Sponsor, monitors and auditors, the FDA, other government offices and the IRB.

Throughout this study, a subject's source data will only be linked to the Sponsor's clinical study database or documentation via a unique identification number. As permitted by all applicable laws and regulations, limited subject attributes, such as sex, age, or date of birth, and subject initials may be used to verify the subject and accuracy of the subject's unique identification number.

The Investigator must agree to permit the Sponsor's monitor or designee's monitor, representatives from any regulatory authority, the Sponsor's designated auditors, and the appropriate IRBs and IECs to review the subject's source data or documents, including, but not limited to, laboratory test result reports, ECG reports, admission and discharge summaries for hospital admissions occurring during a subject's study participation, and autopsy reports. Access to a subject's original medical records requires the specific authorization of the subject as part of the informed consent process. The confidentiality of the verified data and the protection of the subjects must be respected during these inspections.

Copies of any subject source documents that are provided to the Sponsor must have certain personally identifiable information removed.

14.6 Publication, Disclosure, and Clinical Study Registration Policy

The Investigator will provide the Sponsor with truthful, accurate and complete test results and all data derived from the study. During the study, only the Sponsor may make study information available to other study Investigators or to regulatory agencies, except as required by law or regulation. Except as otherwise allowable in the clinical study site agreement, any public disclosure (including publicly accessible websites) related to the protocol or study results, other than study recruitment materials and/or advertisements, is the sole responsibility of the Sponsor.

ProSciento or its designee will be responsible for preparing the Clinical Study Report. When all data has been fully analyzed, ProSciento or Sponsor will communicate the results of the Clinical Study to the Investigator(s).

The Investigator or qualified designee agrees to use this information only and strictly in connection with this Clinical Study and must not use it for other purposes without the prior written permission from the Sponsor. Prior to any publication, the Sponsor must be given the opportunity to review and comment upon any manuscript, poster, or paper that contains data derived or generated from this study in order to be aware of all written and oral presentations of the data and does not imply any editorial review or restriction of the contents of the presentation or use.

To ensure that information on clinical studies reaches the public in a timely manner and to comply with applicable law, regulation and guidance, this study may be registered on Clinicals.gov or other publicly accessible websites before study initiation.

14.7 Insurance and Compensation for Injury

The Sponsor shall carry applicable insurance in the types and amounts necessary to cover its obligations herein in accordance with local laws and requirements and/or guidelines for conducting clinical studies in any country, unless others have shown negligence. The Sponsor renounces liability in the event of negligence or any other liability by the clinics or doctors conducting experiments or by persons for whom the said clinic or doctors are responsible. The Sponsor accepts liability in accordance with all applicable regulations per the Code of Federal Regulations (CFR) and all other applicable federal or state regulations.

Each subject in the study must be insured in accordance with the regulations applicable to the CRU where the subject is participating.

If a subject becomes ill or injured due to an adverse event directly resulting from use of the study drug or a study procedure in the course of their participation in this Clinical Study, medical treatment will be provided. Sponsor will pay the costs of such treatment.

16.0 APPENDIX

Table 16-1 Schedule of Events

ASSESSMENT	SCREEN		IN-HOUSE PERIOD								OUTPA VIS	F/U	
Visit/ Timepoint (Day)	- 28	-2	-1	1	2	3	4	5	6	7	10 (± 1)	17 (± 1)	30 (± 2)
IP Administration				X									
Informed consent	X												
Demography	X												
Medical history	X												
Sequestered in clinic/unit		X	X	X	X	X	X	X	X	X			
Physical examination (PE)	X												X
Abbreviated PE		X								X	X	X	
Hematology, serum chemistry, urinalysis	X		X	X		X				X		X	X
Amylase, Lipase	X		X		X	X	X	X	X		X	X	X
Calcitonin	X												X
Coagulation	X		X			X							
TSH	X												X
HbA1c	X												
Hep B, Hep C, HIV	X												
ADAbs, nAbs & anti-PEG			X									X	X
Pregnancy test (urine)		X									X	X	X
Pregancy test (serum)	X												
FSH if postmenopausal	X												
Urine drug screen & alcohol breath test	Х	X									X	X	X
Weight	X	X	X	X	X	X	X	X	X	X	X	X	X
Height, BMI	X												
Vital signs	X	X	X^1	X^1	X^1	X^1	X ¹	X ¹	X ¹	X ¹	X	X	X
Standardized meals		X	X	X	X	X	X	X	X	X			

ASSESSMENT	SCREEN	IN-HOUSE PERIOD									OUTPA VISI	F/U	
Visit/ Timepoint (Day)	- 28	-2	-1	1	2	3	4	5	6	7	10 (± 1)	17 (± 1)	30 (± 2)
IP Administration				X									
Record concomitant medications	X	X	X	X	X	X	X	X	X	X	X	X	X
Record AE'S	X	X	X	X	X	X	X	X	X	X	X	X	X
Injection site assessment				X^3	X	X	X	X	X	X			
12-lead ECG	X	$X^{2,7}$					$X^{2,7}$	X^7		X^7	X^7	X^7	X^7
Holter monitoring ⁴			X	X	X	X	X						
ABP monitoring ⁴		X	X	X	X	X	X						
PK assessment ⁵				X	X	X	X	X		X	X	X	X
Insulin, C- peptide, glucagon ⁶				X	X	X	X	X		X	X	X	X
GLP-1, GIP, amino acid panel ⁶				X	X	X	X	X		X	X	X	X
FPG	X		X ⁶	X^6	X ⁶	X^6	X^6	X^6	X^6	X^6	X^6	X^6	X ⁶
Lipid panel, incl. FFA	X			X ⁶		X ⁶				X ⁶		X^6	
Leptin ⁶				X		X				X		X	
CRP ⁶	C1.1 1		11.1	X		X		·	1	X	D 1	Х	1

 1 Measurements of blood pressure will be performed twice (morning and evening) on Day -1. On Day 1, measurements will be performed pre-dose and at 4, 8 and 12 hours post-dose, on Day 2 at 24 and 36 hours post-dose, on Day 3 at 48 hours, on Day 4 at 72 hours, on Day 5 at 96 hours, on Day 6 at 120 hours, on Day 7 at 144 hours post-dose with a sampling window of \pm 15 min for each timepoint.

Measurements of pulse rate and respiration rate will be performed at time points together with blood pressure measurements. Pulse rate will be assessed in combination with both, supine and standing blood pressure measurements. Respiration rate will be assessed at time points of supine blood pressure measurements.

²ECG measurements are to be collected on Day -2 before subjects are connected to the ABPM and on Day 4 after subjects have been disconnected from the ambulatory devices.

³Measurements of local injection site reaction on Day 1 at pre-dose, at 4 and 12-hour post-dose.

⁴Timepoints may be adjusted after evaluation of PK data.

⁵Sampling timepoints according to Table 9-2 PK Sampling Schedule.

⁶Sampling timepoints according to Table 9-3 PD Sampling Schedule.

⁷Triplicate ECG's to be performed.

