4.3 Summary of Pre-Clinical Studies

To date, no human studies have been conducted with HM15211.

In vitro activity of HM15211 was evaluated using respective receptors, human GLP-1 receptor (hGLP-1R), human glucagon receptor (hGlucagonR), and human GIP receptor (hGIPR). HM15211 showed dose-dependent activation of all three receptors with potent glucagon activity in addition to balanced GLP-1 and GIP activity. Simultaneous activation of three incretin receptors could provide synergistic metabolic benefits on body weight loss and lipid profile improvement whilst avoiding hyperglycemic risk.

Further in vitro studies confirmed, that since HM15211 includes an aglycosylated Fc moiety derived from human IgG4, it shows minimal immune-mediated effector functions. In addition, due to Fc moiety, HM15211 retained pH-dependent FcRn binding property, which is essential for vascular endothelial recycling.

In vivo pharmacology studies using obese mice showed that HM15211 enables potent body weight loss from both, food intake inhibition and enhanced energy expenditure. The body weight loss was mainly from fat mass reduction, along with lowered serum lipid profile. Glucagon action increased energy expenditure and thus enhanced body weight loss and hyperglycemic risk by glucagon was effectively buffered by actions of GLP-1/GIP. In NASH induced models, HM15211 effectively reduced hepatic triglycerides

(TG), oxidative stress and inflammatory markers. Furthermore, HM15211 treated animals showed significant reduction in NAFLD activity score and hepatic fibrogenic markers, suggesting HM15211 as an effective pharmacotherapy for NASH with hepatic fibrosis.

Safety pharmacology studies were conducted to evaluate the effects on the cardiovascular, respiratory, central nervous systems and in vitro hERG channel assay. No significant effect was observed in the safety pharmacology studies and in vitro human ether-a go-go related gene (hERG) channel assay.

In pharmacokinetic studies, HM15211 exhibited a prolonged half-life (t½) after subcutaneous (SC) or intravenous (IV) dosing, which ranged from approximately 42.7 to 85.6 hours in mice, 74.7 to 86.0 hours in rats, and 35.7 to 79.7 hours in dogs, indicating that HM15211 is a long acting triple-agonist. HM15211 is preferentially distributed in the liver, making HM15211 a favorable treatment option for dysfunction in lipid metabolism specifically in the liver.

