The toxicity studies of HM15211, repeat dose toxicity up to 4 weeks in rats and monkeys, and in vitro genotoxicity studies, were conducted. Local tolerance of HM15211 was investigated in 4-week repeated rat and monkey studies. Additional studies were conducted with HMC001 (inactive ingredient) in rat and monkey up to 4 weeks repeat dose toxicity studies.

No target organ was identified during the 4 weeks repeat dose toxicity studies of HM15211. All changes were completely or partially reversible during the recovery period.

The majority of findings were related to fasting effect or pharmacological effect of glucagon. No adverse test article-related findings at the injection sites were noted. No adverse events were observed in HMC001 studies.

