4.5 Dose Escalation Algorithm

The proposed dose escalation algorithm for HM15211 may include the following steps:

Table 4-2 Sample Allocation and Dose Escalation

Cohorts	Number of Subjects	Treatment Period	
Cohort 1	N=6	HM15211- 0.01 mg/kg	
	N=2	Placebo	
Cohort 2	N=6	$HM15211 \le 0.02 \text{ mg/kg}$	
	N=2	Placebo	
Cohort 3	N=6	$HM15211 \le 0.04 \text{ mg/kg}$	
	N=2	Placebo	
Cohort 4	N=6	$HM15211 \le 0.08 \text{ mg/kg}$	
	N=2	Placebo	
Cohort 5	N=6	$HM15211 \le 0.16 \text{ mg/kg}$	
Conort	N=2	Placebo	

Each subject will be randomized to HM15211 or placebo according to the table above. The dose will be 0.01 mg/kg, based on the body weight measured prior to dosing. For dose calculation and rounding, please refer to the Operational Manual/Pharmacy Manual.

After at least 6 subjects ($n \ge 4$ subjects on active drug HM15211) in each cohort have completed at least Day 10, safety and available PK data will be reviewed and a dose decision/ dose escalation decision for the subsequent cohort will be made by the Sponsor and the Investigator. Doses between cohorts will not exceed a 2-fold increase relative to the specified doses stated in the Table 4-3 above. Following the dose escalation decision, the procedures for the subsequent cohorts will be identical to those described above.

Adjustments to the procedures/cohorts may occur after the review of available safety and PK data:

- Adjustments to the number of study cohorts may occur: Additional cohorts may
 be enrolled and proceed at a higher or a lower dose. If deemed appropriate by the
 investigator and sponsor, there may be more than one cohort investigated at the
 same dose level.
- Adjustments to the 24-hr BP and HR monitoring: After the evaluation of the first cohort, tests may be rescheduled, or measurement periods may be focused on specific days to capture the 24-h measurement around the PK_{peak}.
- Adjustments to the visit schedule: If PK data suggest, additional sampling times and/or outpatient visits may be added to the study schedule.

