5.0 STUDY OBJECTIVES

5.1 Primary Objectives and Endpoints

To assess safety and tolerability of HM15211 after single SC doses, in regard to:

- Incidence of adverse events
- Incidence of clinical laboratory abnormalities (including serum amylase, serum lipase, coagulation, thyroid stimulating hormone (TSH), serum calcitonin)
- Immunogenicity (Anti-drug antibodies [ADAbs], neutralizing anti-drug antibodies [nAbs], anti-polyethylene glycol antibodies [anti-PEG])
- Change from baseline in vital signs (blood pressure, respiratory rate, temperature, and heart rate) measurements
- Incidence and severity of clinical findings on physical examination
- Injection site reaction
- Change from baseline in 12-lead ECG parameters; the primary ECG endpoint will be QTcF
- Blood pressure (BP) assessed by 24-hour ambulatory blood pressure monitoring (ABPM); (Mean day- and night time systolic/diastolic BP)
- Heart rate activity assessed by 24-hour ambulatory electrocardiography monitoring (Holter ECG); (Heart rate [HR] and heart rate variability [HRV], e.g. mean heart rate, difference between day and night HR, mean normal [NN] intervals, standard deviation of all NN intervals [SDNN])

To assess the pharmacokinetic (PK) profile of HM15211 after single SC doses in regards, but not limited to:

- Maximum concentration (C_{max})
- Time to reach Cmax (T_{max})
- Total area under the concentration time curve (AUC), including AUC_(0-inf)
- Apparent terminal half-life (t_{1/2})
- Apparent clearance (CL/F)
- Apparent volume of distribution at terminal phase (Vz/F)
- Terminal elimination rate constant (k_{el})

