6.0 STUDY DESIGN AND DESCRIPTION

6.1 Study Design

This is a first-in-human, randomized, double-blind, SAD study to evaluate the safety, tolerability, and PK of HM15211 as primary objectives in healthy obese subjects.

The study will be conducted in five sequential cohorts (cohort 1 to 5) comprising a total of up to approximately 40 subjects. Each cohort will enroll subjects to ensure that at least 8 subjects per cohort will complete the study. Drop-outs may be replaced in order to have 8 completed subjects in each cohort. Subjects will be allocated into sequential dosing cohorts based on their order of entry into the study and be randomized to investigational product (IP) or placebo in a 3:1 ratio, with 6 subjects on IP and 2 subjects on placebo. Cohorts may partially overlap after at least 6 subjects have completed at least D10 and a dose escalation decision has been made.

Dosing will follow a sentinel approach with the dosing between the first 2 subjects (1 on active, 1 on placebo) and the remainder of the cohort at least 24 hours apart. A minimum of 10-days between the start date of consecutive dose levels will be maintained. Based on available safety, tolerability, and PK data of each cohort, and following a safety review and dose escalation meeting between the investigator and the sponsor, dose escalation to the next cohort may proceed. If dose escalation is stopped (please see dose escalation stopping criteria in section 6.4.1), dose de-escalation may occur in additional cohorts, to further refine clinically relevant dose levels.

Each subject will undergo a screening visit, followed by one in-house/ treatment period per subject. Two additional outpatient visits will occur, prior to a final follow-up visit that will conclude subject study participation.

The duration of subject participation in this study, including screening, treatment and follow-up will approximately be 9 weeks for subjects.

Figure 6-1 Study Design Schematic

[figure not shown]
[figure not shown]

Figure 6-2 Dose Escalation Schematic

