6.3 Rationale for Study Design and Endpoints

This SAD study will assess the safety and tolerability as well as PK of HM15211 as primary objectives.

Cohorts will be assessed in ascending order, but may overlap, to determine a clinically appropriate dose for the subjects and will include the comparison with placebo.

Randomization is used to avoid bias introduced through an association between study drug allocation order and subject characteristics.

A double-blind design has been chosen to avoid bias and to maintain the blind between the administration of the study drug and placebo.

Healthy obese subjects will participate in the study, as these subjects are an important target population for the novel triple agonist. Enrollment criteria will favor the target population, as body mass index will be limited to ≥ 30 to ≤ 40 kg/m².

After PK modeling, C_{max} is expected to be reached approximately 3 days after dosing. As this is a first-in-human study, measurements for the assessment of cardiovascular events will start right after dosing and will continue until Day 4. After evaluation of the PK values in the initial cohort(s), the monitoring period will be adjusted, to ensure that the 24-h period around the PK_{peak} is captured.

The proposed PK endpoints are well-established, commonly used parameters to characterize pharmacological profiles of drugs. For the PK endpoints, blood samples for determination of HM15211 will be analyzed using a validated assay.

This is an exploratory study. No formal sample size calculation and no statistical hypothesis testing will be performed.

The study will be conducted at a specialized early phase research centre, where the subjects will be under supervision of physicians, research nurses and additional medical staff experienced in conducting early phase clinical studies investigating new metabolic compounds.

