6.4 Study Discontinuation and Stopping Criteria

6.4.1 Dose Escalation Stopping Criteria

Dose escalation will be stopped if one of the following conditions apply:

• Death of a subject (AE grade 5 toxicity) in one cohort, at any time, that is considered related to the IP, judged by the Investigator

- One subject in a cohort develops an AE ≥ Grade 3 toxicity, that is considered related to the IP, judged by the Investigator
- One subject in a cohort develops an AE Grade 2 toxicity that persists for more than 7 days and is considered related to the IP, judged by the Investigator
- 2 or more of the subjects in a cohort have experienced severe adverse events, judged to be possibly or probably related to the IP, judged by the Investigator;
- 2 or more subjects receiving HM15211 develop similar clinically significant laboratory, significant ECG or vital signs abnormalities, or severe AEs in the same organ class, indicating dose-limiting intolerance. Dose escalation may proceed if after review of the data by the Investigator and discussion with Sponsor, it is concluded that the events are not drug related;
- It is determined that the limit of safety and/or tolerability has been reached. Decision will be made between Sponsor and Investigator.

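### Day 10 gates dose escalation but has no haematology or serum chemistry in Table 16-1; adding that panel is a cheap improvement, not the correction of an error

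*Protocol*

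**What the plan says.** Protocol Section 16.0, Table 16-1, marks the row "Hematology, serum chemistry, urinalysis" at Screening and on Days -1, 1, 3, 7, 17 and 30. Day 10 is blank. Table 9-1 (Section 9.1.8) places the blood count under haematology, and the hepatic panel and the renal panel with electrolytes under serum chemistry.

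Section 4.5 sets the gate. Once at least 6 subjects, at least 4 of them on HM15211, "in each cohort have completed at least Day 10, safety and available PK data will be reviewed" and the next dose is chosen, at most a doubling. Section 6.1 adds: "A minimum of 10-days between the start date of consecutive dose levels will be maintained".

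Laboratory data count in that decision. "Incidence of clinical laboratory abnormalities" is a primary endpoint (Section 5.1). Under Section 6.4.1 escalation stops if 2 or more subjects on HM15211 "develop similar clinically significant laboratory, significant ECG or vital signs abnormalities", unless the events are judged not drug related.

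Section 6.3 states that the peak concentration "is expected to be reached approximately 3 days after dosing".

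**The concern.** The visit that opens the escalation decision supplies no scheduled liver, kidney or blood-count value. The reviewers would rely on Day 7 results, and the next panel may be drawn only after the next cohort has begun a dose up to twice as high. A change that causes no symptoms and first appears after Day 7 could not trigger the laboratory stopping rule in time.

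The protocol gives some reason to want current hepatic values in particular: Section 4.3 describes preferential distribution of the drug to the liver, and half-lives in animals of up to about 86 h.

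**Working it through.** **Inputs.** Visit times come from Section 9.1.6, the panel days from Table 16-1, the gate from Section 4.5, the minimum spacing and sentinel interval from Section 6.1, the predicted peak from Section 6.3, the half-lives from Section 4.3 and the blood volumes from Section 9.1.20.

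**1. Visit times.** Nominal hour = (Day - 1) x 24. Day 3 = 48 h, Day 7 = 144 h, Day 10 = 216 h and Day 17 = 384 h, which matches the hours in Section 9.1.6. Days 10 and 17 have a window of ± 24 h.

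**2. Age of the newest panel at the Day 10 visit.** 216 - 144 = 72 h. With the window, 192 - 144 = 48 h to 240 - 144 = 96 h.

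**3. Gap across the gate.** 384 - 144 = 240 h. With a Day 10 panel it splits into 216 - 144 = 72 h and 384 - 216 = 168 h.

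**4. Can the next dose level start before Day 17?** The 10-day minimum is 10 x 24 = 240 h after the first dose. The gate can be met by then: subjects dosed 24 h after the sentinel pair reach nominal Day 10 at 24 + 216 = 240 h. The sentinel pair's Day 17 panel comes 384 - 240 = 144 h later (360 - 240 = 120 h to 408 - 240 = 168 h with the window). This is the earliest case and allows no time for the review itself.

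**5. Exposure left at Day 10 (assumed model).** The protocol gives no human profile. Assume one compartment with first-order absorption, C(t) proportional to exp(-ke t) - exp(-ka t), ke = ln 2 / half-life, and ka chosen so that the peak falls at Tmax. Half-life runs over the animal range: Section 4.3 gives "74.7 to 86.0 hours in rats, and 35.7 to 79.7 hours in dogs", and the mouse range lies inside the overall 35.7 to 86.0 h.

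| Tmax | Day 3 (48 h) | Day 7 (144 h) | Day 10 (216 h) |
|---|---|---|---|
| 72 h | 93% | 74% to 77% | 41% to 47% |
| 60 to 84 h | 88% to 98% | 59% to 86% | 27% to 59% |

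Values are percentages of peak. Check of the low end, where ka = ke and the fraction is (t/Tmax) exp(1 - t/Tmax): at Tmax 60 h, 3.6 x exp(-2.6) = 0.267. Check of the high end, Tmax 84 h and half-life 35.7 h: ke = 0.01942, ka = 0.00664 per hour, C(216)/C(84) = 0.2234/0.3769 = 0.593. At that corner absorption is slower than elimination.

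**6. Subjects and decisions affected.** Five cohorts give 5 - 1 = 4 planned escalation decisions, resting on cohorts 1 to 4: 4 x 6 = 24 active subjects. Cohort 5 is not counted because no higher dose is planned after it.

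**7. Blood volume.** The planned total is about 370 mL, rising to about 400 mL with unforeseen sampling, so 30 mL is in reserve. At an assumed 5 to 15 mL per panel (not given in the protocol), one added panel makes 375 to 385 mL and uses 5/30 = 17% to 15/30 = 50% of the reserve.

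**The case against.** The strongest reply is that the schedule follows a stated logic and already covers most of the risk.

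- The version 2.0 entry in Section 1.3 explains the Day 10 gate by saying that dose-limiting events occur at or around the peak. The Day 3 and Day 7 panels lie on either side of it.
- Section 9.1.8 requires every clinically significant laboratory abnormality to be recorded as an adverse event. Section 10.4.1 requires subjects with adverse events to be monitored until relevant laboratory changes return to baseline or are satisfactorily explained. Anything significant found by Day 7 is therefore followed without a fixed Day 10 panel.
- Day 10 already has amylase and lipase, fasting glucose, vital signs, triplicate ECG, an abbreviated physical examination and adverse event recording.
- For the animal studies, Section 4.3 reports: "No target organ was identified during the 4 weeks repeat dose toxicity studies of HM15211".

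All of this stands and it narrows the point. It does not reach a new, silent change after Day 7, because follow-up duties begin only once something has been found. The retesting in Section 9.1.8 and the PK-driven extra sampling in Section 4.5 are optional and fix no panel.

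A reader might also infer that a Day 4 panel is needed because none is drawn at the predicted 72 h peak. The documents do not support that. Under the model in the working, the Day 3 panel falls at 88% to 98% of peak and the Day 7 panel at 59% to 86%, so a Day 4 panel would add little.

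**Conclusion.** The point holds as a modest improvement to the design. A reader might infer that the protocol breaks its own rules or escalates without laboratory data. It does neither: no section promises a full panel on Day 10, and the Day 3 and Day 7 panels precede the decision.

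The remaining gap is a hepatic, renal or haematological change without symptoms that first appears after Day 7, at a time when exposure may still be material. The panel times and gaps follow directly from the protocol. The exposure range rests on the assumed one-compartment model, animal half-lives and a Tmax within 12 h of the prediction, so it is indicative only. The risk is limited, but the decision concerned can double the dose in a first-in-human trial and the remedy costs little.

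**What to change.** 1. In Table 16-1, mark haematology and serum chemistry (hepatic and renal/electrolyte panels) on Day 10, using the blood draw already scheduled for amylase/lipase, fasting glucose and PK. Urinalysis can stay as it is.
2. In Section 4.5, require that the Day 10 results of the subjects reviewed, at least 6, are available before the escalation decision. Without this, the mark in the table does not ensure that the review sees them.
3. In Section 9.1.20, restate the planned blood volume (about 375 to 385 mL on the assumed panel volume).

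The cost is one routine panel per subject, a few millilitres of blood within the existing allowance, and possibly a short wait for results before each decision. No new visit or venepuncture is needed. No Day 4 panel is proposed.
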